# 4.3. Hypothesis

### Primary endpoint hypothesis:

*Null hypothesis:* No difference in self-reported hearing aid benefit (Abbreviated Profile of Hearing Aid Benefit) between the Lexie self-fit group (p0) and audiologist-fit (p1) group at 2-and 6-weeks from baseline, i.e., p1 = p0

Alternative Hypothesis (2-sided): The self-reported hearing aid benefit (Abbreviated Profile of Hearing Aid Benefit) of the Lexie self-fit group (p1) at 2- and 6- weeks will be non-inferior to the audiologist-fit group (p0), within 16.3 (smallest observable change for the APHAB), i.e., p0 – p1  $\leq$  16.3. The non-inferiority margin (- $\Delta$ NI) was arbitrarily decided and is defined as the degree of hearing benefit (%) change for the smallest observable change on the scales.

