### Secondary endpoint hypothesis:

*Null hypothesis*: No difference in self-reported benefit for the Lexie self-fit group (p1) at 2- and 6-weeks and audiologist fit hearing aids (p0) using the International Outcome Inventory for Hearing Aids (IOI-HA), i.e., p1 = p0

Alternative hypothesis (2-sided): The self-reported improvement (IOI-HA) of the Lexie self-fit group (p1) at 2- and 6-weeks will be non-inferior to the audiologist fit group, within 1 point on all scales (smallest observable difference on each scale). i.e.,  $p0 - p1 \le 1$ . This non-inferiority margin (- $\Delta$ NI) was decided based on the critical difference score reported for the IOI-HA  $^4$ .

*Null hypothesis:* No difference in speech recognition in noise (QuickSIN and DIN) improvement between the Lexie self-fit group and audiologist-fit group at 2- and 6- weeks), i.e., p1 = p0

Alternative hypothesis: The improvement of speech recognition in noise for the Lexie self-fit group at 2- and 6- weeks will be non-inferior to the audiologist-fit hearing aid using the QuickSIN and digits-in-noise test (DIN), within 1.8 dB SNR. The non-inferiority margin ( $-\Delta$ NI) is based on the critical difference score of the QuickSIN  $^5$ , i.e.,  $p0 - p1 \le 1.8$ .

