# 5. Statistical analyses

# 5.1. Level of statistical significance

Final analyses of the primary and secondary outcomes will be analysed using a two-sided significance level of 5%.

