# Self-reported hearing aid difficulties

Primary endpoint analyses include the self-reported benefit using the APHAB. Benefit is determined by calculating the APHAB scores conducted at the aided assessment (2-week and 6-week follow-ups) from the baseline scores. The primary endpoint data for all the scores measured at all time points (raw scores), along with the calculated benefit scores (unaided-aided) will be continuous variables. Data will be assessed for normality using the Shapiro Wilk's test. For non-normally distributed variables, non-parametric comparisons between groups will be completed using the Mann Whitney *U* test. For normally distributed variables, comparisons will be done using the independent samples *t*-test.

Effect sizes will be calculated for normally distributed variables, where differences were significant. Cohen's *d* is the primary metric for determining effect sizes of normally distributed variables, for which the values of 0.8, 0.5 and 0.2 are interpreted as large, medium and small effect sizes, respectively. The following formula will be used:

$$d = \frac{M1 - M2}{SDpooled}$$

Effect sizes for non-normally distributed variables will be calculated using effect size *r* for non-parametric tests, calculated using the following formula:

$$z/\sqrt{N}$$

IOI-HA (secondary endpoint) will be conducted at 2- and 6-weeks post hearing aid fitting. IOI-HA data are ordinal response categories and will, therefore, be analysed using non-parametric Mann Whitney U tests for comparison between the two groups.

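### Section 4.3 states non-inferiority alternatives with margins, but section 5 plans only difference tests, so the primary alternative is never tested

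*Combined protocol and SAP*

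**What the plan says.** All references are to the combined protocol and SAP.

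- **Section 4.3, primary alternative.** Self-fit "will be non-inferior to the audiologist-fit group (p0), within 16.3 (smallest observable change for the APHAB"). The margin "was arbitrarily decided and is defined as the degree of hearing benefit (%) change for the smallest observable change on the scales".
- **Section 4.3, primary null.** "No difference in self-reported hearing aid benefit (Abbreviated Profile of Hearing Aid Benefit) between the Lexie self-fit group (p0) and audiologist-fit (p1) group", that is, equality. Self-fit is labelled p0 here but p1 in the alternative.
- **Section 4.3, secondary alternatives.** IOI-HA is to be non-inferior "within 1 point on all scales (smallest observable difference on each scale"). Speech-in-noise improvement "will be non-inferior to the audiologist-fit hearing aid using the QuickSIN and digits-in-noise test (DIN), within 1.8 dB SNR". Both are again paired with equality nulls.
- **Section 5.1.** "Final analyses of the primary and secondary outcomes will be analysed using a two-sided significance level of 5" per cent.
- **Section 5.3, APHAB and speech in noise.** Normality is checked first. "For normally distributed variables, comparisons will be done using the independent samples" *t*-test; otherwise Mann-Whitney *U* is used.
- **Section 5.3, IOI-HA.** "IOI-HA data are ordinal response categories and will, therefore, be analysed using non-parametric Mann Whitney U tests for comparison between the two groups".
- **Section 5.3, effect sizes.** Cohen's *d* is limited to normally distributed variables with a significant difference. For non-normal variables, r = z/√N is given.
- **Section 5.4.** The missing-data check judges by p-values whether the conclusion changes.
- **Section 3.3.** The target is 60 participants, about 30 per group, taken from the size of an earlier over-the-counter trial. No SD, power or expected difference is given.

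**The concern.** The hypotheses ask whether self-fit is worse by no more than a stated amount. The analysis asks whether the groups differ at all. The margins and the 5% level are both fixed in advance, but nothing in section 5 joins them.

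Whoever reports the trial must therefore supply the link after the data are in: an interval, a shifted test, or a reading of the difference test. That choice can change the conclusion. As written, the 5% level belongs to the difference test and does not control the risk of wrongly calling self-fit non-inferior.

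**Working it through.** **Step 1: what each planned result says about the alternative.** The primary alternative is that audiologist-fit (AF) minus self-fit (SF) benefit is at most 16.3. The null, a difference of 0, lies inside that alternative, so the two are not complements.

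| Result of the planned test | Does it decide the primary alternative? |
|---|---|
| Significant, SF better | Yes, SF is non-inferior |
| Significant, SF worse | No, the deficit may be inside or outside 16.3 |
| Not significant | No, the interval may or may not reach 16.3 |

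The planned effect sizes do not fill the gap. Cohen's *d* is absent when the groups look similar, and neither *d* nor r is in APHAB points, IOI-HA points or dB.

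**Step 2: where the two questions part.** Inputs: 30 per arm (section 3.3), margins from section 4.3, two-sided 5% (section 5.1). Every SD is an assumption. The plan has no power or SD figure to reproduce.

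Half-width of the 95% CI = t(0.975; 58 df) × SD × √(2/30) = 2.0017 × 0.2582 × SD = 0.5168 × SD.

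An observed deficit is significant if it exceeds the half-width. It meets a margin rule if it is below 16.3 minus the half-width.

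| SD | Half-width | 16.3 − half-width | Observed deficits between the two cut-offs |
|---|---|---|---|
| 10 | 5.17 | 11.13 | 5.17 to 11.13: significantly worse, yet non-inferior |
| 15 | 7.75 | 8.55 | 7.75 to 8.55: significantly worse, yet non-inferior |
| 20 | 10.34 | 5.96 | 5.96 to 10.34: not significant, non-inferiority not shown |
| 25 | 12.92 | 3.38 | 3.38 to 12.92: not significant, non-inferiority not shown |
| 30 | 15.51 | 0.79 | 0.79 to 15.51: not significant, non-inferiority not shown |

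The cut-offs coincide only when the half-width is half the margin: SD = 8.15/0.5168 = 15.77 for APHAB, and 0.9/0.5168 = 1.74 dB for the 1.8 dB margin.

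**Step 3: how often this happens** (400,000 simulated trials per cell, normal data, one visit). *Both* means significantly worse and upper limit below 16.3. *Neither* means not significant and upper limit at or above 16.3.

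| SD | True deficit 8: both | True deficit 8: neither | No difference: both | No difference: neither |
|---|---|---|---|---|
| 10 | 0.746 | 0.000 | 0.025 | 0.000 |
| 15 | 0.112 | 0.026 | 0.013 | 0.003 |
| 20 | 0.0005 | 0.316 | 0.0001 | 0.101 |
| 25 | 0.000 | 0.528 | 0.000 | 0.275 |
| 30 | 0.000 | 0.645 | 0.000 | 0.432 |

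At SD 15 the two add to only about 14% (0.112 + 0.026) at a deficit of 8, and 1.6% (0.013 + 0.003) with no difference.

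**Step 4: if a non-significant result were read as non-inferior.** The plan does not say this. If it were done with a true deficit of 16.3, the error rate would be P(|T| < 2.0017), where T is noncentral t with 58 df and noncentrality 16.3/(SD × 0.2582). This gives 1.5%, 12.6%, 30.0% and 45.6% at SD 15, 20, 25 and 30. A margin test holds it at 2.5%.

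**The case against.** The strongest reply is that the simulated rates are not errors made by the plan. A result can properly be both significantly worse and non-inferior, and *neither* would remain after the fix as non-inferiority not shown. That stands: the rates show how often the two questions have different answers, not how often the plan is wrong. The Step 4 error rates also depend on a reading the plan never adopts, and at SD 15 that rate (1.5%) is below 2.5%.

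Other points:

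- Section 5.4 describes a missing-data check, not the primary decision. This is fair; it is supporting evidence only.
- Section 5.3 speaks only of comparisons and does not say that the tests are unshifted. The equality nulls in section 4.3 make that the natural reading, and no shift is mentioned anywhere.
- Software may print a confidence interval with the *t*-test. The plan does not say it will be used or set against a margin, and the Mann-Whitney analyses, including all of IOI-HA, specify no interval.
- A margin rule for IOI-HA treats ordinal categories as equally spaced. This is a real cost, but the plan's own 1-point margin already implies it.
- If the normality check still selects the method, a mean difference may be compared with the margin at one visit and a Hodges-Lehmann shift at another. This stands as a limitation of the remedy.

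None of these supplies the missing test of the primary alternative.

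**Conclusion.** The concern holds, with high confidence, and must be fixed. The plan as written does not test its own primary alternative, and the same gap affects IOI-HA, QuickSIN and DIN. This follows from setting section 4.3 beside section 5 and needs no assumed figure.

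The practical size depends on unknown SDs. With 30 per arm, the two questions give nearly the same answer around an APHAB SD of 15 to 16 and move apart on either side. The plan does not equate a non-significant result with non-inferiority; it gives no rule either way.

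**What to change.** 1. **Section 4.3.** Use one labelling throughout. Set H0: AF − SF ≥ margin and H1: AF − SF < margin, on the benefit scale (unaided minus aided) for APHAB, QuickSIN and DIN, and on the score for IOI-HA.
2. **Section 5, continuous endpoints.** Report AF − SF with a two-sided 95% CI whatever the p-value. Declare non-inferiority only if the upper limit is below the margin. Use a Hodges-Lehmann interval on the non-parametric route.
3. **Section 5, IOI-HA.** Name one rule in advance: a Mann-Whitney test on scores shifted by 1 point (one-sided 2.5%, closest to the current plan), or the upper 95% limit for the mean difference below 1. Avoid a Hodges-Lehmann limit here, because on integer categories it takes only integer values.
4. **Scope.** Confirm whether both the 2-week and 6-week results must pass, and name the APHAB score or scores to which 16.3 applies.
5. **Interpretation.** State that a non-significant difference test is not evidence of non-inferiority. Repeat beside the rule that the plan itself calls the 16.3 margin arbitrary.

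**Cost.** Wording and one interval or shifted test per endpoint; no new assessments. The downsides below assume no true difference and 30 per arm.

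| Assumed APHAB SD | Power, one visit | Power, both visits (correlation 0.5 to 0.8, assumed) |
|---|---|---|
| 15 | 98.5% | 97–98% |
| 20 | 87% | 80–82% |
| 25 | 70% | 56–60% |
| 30 | 54% | 37–44% |

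For one IOI-HA scale at one visit (five assumed categories, SD 0.93 to 1.26), the pass rate falls from 99% to 81% for the shifted Mann-Whitney test and from 98% to 85% for the mean-difference interval. A Hodges-Lehmann limit would pass only 60% to 31%. Passing all scales at both visits would be less likely. With scores kept within 1 to 5 and a mean 1 point lower, simulated false non-inferiority was 1.2% to 3.0% for the shifted test, slightly above 2.5% at worst, and 2.0% to 2.4% for the mean-difference interval.

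The rule also turns an admittedly arbitrary margin into a pass/fail line.

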# Behavioral outcome measures

Speech recognition scores will be conducted at baseline and at the 2- and 6-week follow ups. Raw scores will be gathered (continuous variables). Additionally benefit scores will be determined by subtracting aided from aided scores. All variables are continuous and will be assessed for normality. For non-normally distributed variables, non-parametric comparisons between groups will be completed using the Mann Whitney *U* test. For normally distributed variables, comparisons will be done using the independent samples *t*-test.

Effect sizes will be calculated for normally distributed variables, where differences were significant. Cohen's *d* is the primary metric for determining effect sizes of normally distributed variables, for which the values of 0.8, 0.5 and 0.2 are interpreted as large, medium and small effect sizes, respectively. The following formula will be used:

$$d = \frac{M1 - M2}{SDpooled}$$

Effect sizes for non-normally distributed variables will be calculated using effect size r for non-parametric tests, calculated using the following formula:

$$z/\sqrt{N}$$

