### 4.2. Behavioral outcome measures

Participants of both groups will participate in the following speech recognition in noise assessments to be conducted as unaided at the pre-field trial stage and as aided at both the post-field trials.

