### 4.2.1. QuickSIN

Several aspects of the QuickSIN test make it suitable for use in assessing comparable improvement of speech-in-noise performance. (1) It is designed to be presented above average conversational level (2) It uses a wide range of SNRs, and (3) the multi-talker background noise represents a common and challenging communication situation. QuickSIN is reported in terms of SNR loss, the increase in SNR required to understand speech in noise compared to persons with normal hearing; higher SNR loss indicates a poorer outcome (4).

SNR loss will be measured unaided at the initial assessment for all participants (prior to the random allocation process). Twice thereafter the aided SNR Loss will be measured. The first aided measurement as per initial fitting settings at the 3rd visit following the post 2-week field trial for the AF and SF groups. The second SNR loss will be measured with

the hearing aids set to the user's preferred setting at the 4th visit, post the 6-week field trial for both groups.

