# 4.2.2. Digits-in-Noise

Since the QuickSIN was developed in American English, one concern was that South African participants could have difficulty recognizing the words due to differences in dialect. Therefore, in addition to the QuickSIN, speech-in-noise performance will be measured using the South African English Digits-in-Noise test (DIN) (5,6). The DIN unaided and aided results will be measured following the same procedure as set for performing the QuickSIN).

Table 1. Timing of the assessments						
Visit	Baseline	Hearing Aid Fitting	2-week follow- up	6-week follow- up		
Pure tone audiometry	Х					
APHAB	X		Х	X		
IOI-HA			X	X		
QuickSIN	X		Х	Х		
DIN	X		X	X		
Real-Ear Measurement		Х		Х		

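### The QuickSIN and DIN benefit score is written with two aided terms and no unaided baseline, so it does not give the improvement at 2 and 6 weeks that the secondary hypothesis tests.

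*Combined protocol and SAP*

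**What the plan says.** Section 5.3, under Behavioral outcome measures, begins with the schedule: "Speech recognition scores will be conducted at baseline and at the 2- and 6-week follow ups". It keeps the raw scores as continuous variables and then adds the derived score: "Additionally benefit scores will be determined by subtracting aided from aided scores". Group comparisons follow, by independent-samples t-test or Mann-Whitney U test according to normality. No other section defines a speech-in-noise benefit score.

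The measurement sections are clear about what is collected:

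- Section 4.2 has the speech tests done "unaided at the pre-field trial stage and as aided at both the post-field trials".
- Section 4.2.1 says of QuickSIN: "SNR loss will be measured unaided at the initial assessment for all participants". This precedes random allocation. One aided measurement follows at the third visit (initial fitting settings) and one at the fourth (the user's preferred settings). On direction: "higher SNR loss indicates a poorer outcome".
- Section 4.2.2 carries this over: "The DIN unaided and aided results will be measured following the same procedure as set for performing the QuickSIN".

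Section 4.3 states the hypothesis on improvement: "The improvement of speech recognition in noise for the Lexie self-fit group at 2- and 6- weeks will be non-inferior". The margin is 1.8 dB SNR, written as p0 − p1 ≤ 1.8.

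**The concern.** A benefit score for a hearing aid compares performance without the aid to performance with it. The written rule has an aided score on both sides of the subtraction and names no visits, so it does not compute the quantity named in the secondary hypothesis.

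At stake is the operative definition of the benefit score for two secondary endpoints. If the sentence stays, the analyst must decide which of the two aided terms was meant to be unaided, and that choice sets the sign of the score. The hypothesis is one-directional (p0 − p1 must not exceed 1.8), so the sign should be fixed in the plan.

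**Working it through.** **1. Scores available, per participant and per test** (sections 4.2 to 4.2.2 and Table 1)

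| Visit | Condition | Symbol |
|---|---|---|
| Baseline | unaided | U |
| 2-week follow-up | aided, initial settings | A2 |
| 6-week follow-up | aided, preferred settings | A6 |

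Table 1 shows no speech test at the fitting visit. There is therefore one aided score per test at each follow-up.

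**2. Scores the hypothesis needs** (section 4.3)

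Improvement at 2 weeks is U − A2, and at 6 weeks U − A6. Two tests × 2 follow-ups = 4 scores per participant.

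**3. Scores the written rule can give** (section 5.3)

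With only aided terms, the one usable pair is A2 and A6, which gives one change per test, or 2 values per participant. Neither uses U, and neither exists at the 2-week visit. By section 4.2.1 this change runs from initial to preferred settings. That is a coherent quantity, but a different one.

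**4. One participant, QuickSIN** (values assumed for illustration): U = 8, A2 = 4, A6 = 3 dB.

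- Intended: 8 − 4 = 4 dB at 2 weeks and 8 − 3 = 5 dB at 6 weeks.
- As written: 4 − 3 = 1 dB, once, with the order of subtraction unstated.

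**5. Evidence of intent**

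The APHAB paragraphs of section 5.3 give benefit as unaided minus aided. The speech paragraph lists the baseline among its scores. The hypothesis speaks of improvement. All three point to U − A.

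**6. Why the sign must be written down**

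The speech hypothesis does not define p0 and p1. The IOI-HA hypothesis just above it has p0 = audiologist-fit and p1 = self-fit, and those labels are used here. Assumed QuickSIN means: unaided 8 dB in both arms; aided 4 dB audiologist-fit and 7 dB self-fit.

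- Unaided minus aided: benefits 8 − 4 = 4 and 8 − 7 = 1; p0 − p1 = 4 − 1 = 3, outside 1.8.
- Aided minus unaided: 4 − 8 = −4 and 7 − 8 = −1; p0 − p1 = −4 − (−1) = −3, inside 1.8 although self-fit is 3 dB worse.

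Both orders repair the sentence grammatically. Only the first matches the APHAB definition and gives the rule its intended direction.

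**7. What the raw scores still provide**

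The between-arm difference in benefit is (U_AF − A_AF) − (U_SF − A_SF). U is measured before random allocation, so its expected value is equal in the two arms and the expression reduces in expectation to A_SF − A_AF. In the example, 7 − 4 = 3. The raw aided comparison thus estimates the same contrast with the sign reversed (4 − 7 = −3).

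**The case against.** The strongest reply is that this is one mistyped word and the document resolves it. The baseline is collected, the parallel APHAB score is spelled out, the hypothesis says improvement, and the speech paragraph itself lists the baseline visit. Because of randomisation, the raw aided comparison also targets the same between-arm contrast, so baseline subtraction affects precision and chance imbalance rather than what is compared. All of this stands, and it limits the weight of the point. It does not make the sentence correct. This is an operative endpoint rule, and the APHAB wording, though a good guide, does not formally govern QuickSIN or DIN.

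Some stronger readings are tempting but unsupported:

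- A reader might infer that the rule makes every benefit score zero. That would require subtracting a score from itself, since no second aided score per test is scheduled at any follow-up.
- A reader might infer that the 1.8 dB rule would be applied to raw SNR loss and so favour a worse self-fit arm. Section 4.3 states both the null and the alternative on improvement, which excludes that use.
- A reader might infer that 1.8 dB is the wrong margin for the DIN. The plan takes it from the QuickSIN critical difference, but nothing in the documents shows that it is too wide or too narrow. That is a separate matter.

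It is also fair to say that the t-tests and Mann-Whitney tests in section 5.3 make no use of the margin. Correcting this sentence does not by itself supply a non-inferiority analysis.

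**Conclusion.** The point holds as an error in a definition. The only rule for the speech-in-noise benefit score omits the unaided baseline. It gives none of the 4 scores per participant that the hypothesis calls for, and at most 2 values of a different quantity.

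The consequence is modest. It reaches the benefit-score analyses of two secondary endpoints only. No measurement is missing, the raw-score comparisons stand, the APHAB score definition is unaffected, and no sample-size or significance figure changes. A reader might infer that speech-in-noise improvement cannot be analysed in this trial; the documents do not support that, because the data are collected and the intent is recoverable.

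The counts follow from the schedule in the documents. The dB examples rest on assumed values and illustrate only the mechanism and the sign. The sign argument also assumes that the p0 and p1 labels of the IOI-HA hypothesis carry over to the speech hypothesis. For QuickSIN, the direction of the score is stated. For the DIN it is not.

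**What to change.** In section 5.3, Behavioral outcome measures, replace the sentence with: *Benefit = unaided baseline score minus aided score, calculated separately at the 2-week and 6-week follow-ups, for QuickSIN and DIN.*

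Add that a positive value means improvement. For QuickSIN this follows from the direction given in section 4.2.1; state the DIN score direction in the same way so that its sign is fixed too.

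In section 4.3, state for the speech hypothesis that p0 is audiologist-fit and p1 is self-fit, and that p0 − p1 ≤ 1.8 refers to this benefit score.

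The cost is one replaced sentence and one or two clarifying ones. No new measurements are needed, and no change to the DIN margin forms part of this point. The correction should be made before the benefit scores are analysed, so that the definition and its sign are set by the plan.
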